### **6.3 Modification in Dose or Schedule**

To limit myelosuppressive toxicity, Cycles 3 and beyond will consist of 20 mg/m^2/day for 5 consecutive days (Days 1-5).

## **7.0 REGULATORY AND REPORTING REQUIREMENTS**

The entities providing oversight of safety and compliance with the protocol require reporting as outlined below.

Please refer to Appendix A for definitions and Appendix C for a grid of reporting timelines. Adverse events will be tracked from the time of consent until 30 days after the last dose of chemotherapy. Adverse events will be tracked from the time of consent until 30 days after the last

dose of chemotherapy. All adverse events must be recorded on the toxicity tracking case report form (CRF) with the exception of baseline adverse events, which shall be recorded on the medical history CRF.

Refer to the data submission schedule in Section 11 for instructions on the collection of AEs in the EDC.

Reporting requirements for Washington University study team may be found in Section 1.1. Reporting requirements for secondary site study teams participating in Washington University-coordinated research may be found in Section 1.2.

The safety and side effects of decitabine have been well characterized in numerous clinical trials involving patients with AML and MDS. In specific, cytopenias are commonplace in patients with AML and in patients treated with decitabine. These frequently result in infection complications, bleeding complications, and transfusion requirements.

Janssen requires that all events be reported as outlined in Section 7.5.

### **7.1 Reporting to the Human Research Protection Office (HRPO) at Washington University**

Reporting will be conducted in accordance with Washington University IRB Policies.

Pre-approval of all protocol exceptions must be obtained prior to implementing the change.

### **7.2 Reporting to the Quality Assurance and Safety Monitoring Committee (QASMC) at Washington University**

The Washington University Sponsor-Investigator (or designee) is required to notify the QASMC of any unanticipated problems involving risks to participants or others occurring at WU or any BJH or SLCH institution that has been reported to and acknowledged by HRPO. (Unanticipated problems reported to HRPO and withdrawn during the review process need not be reported to QASMC.)

QASMC must be notified within **10 days** of receipt of IRB acknowledgment via email to [[contact]](mailto:[contact]). Submission to QASMC must include the myIRB form and any supporting documentation sent in with the form.

For events that occur at secondary sites, the Washington University Sponsor Investigator (or designee) is required to notify the QASMC within 10 days of Washington University notification via email to [[contact]](mailto:[contact]). Submission to QASMC must include either the myIRB form and supporting documentation or (if not submitted to myIRB) the date of occurrence, description of the event, whether the event is described in the currently IRB approved materials, the event outcome, determination of relatedness, whether currently enrolled participants will be notified, and whether the informed consent document and/or any study procedures will be modified as a result of this event.

### 7.3 Secondary Sites Reporting Requirements

The research team at each secondary site is required to promptly notify the Washington University Sponsor-Investigator and designee of all serious adverse events (refer to Appendix A, Section D) within **1 working day** of the occurrence of the event or notification of the secondary site's PI of the event. This notification may take place via email if there is not yet enough information for a formal written report using an FDA Form 3500a (MedWatch form) and Washington University's Cover Sheet (Appendix C). A formal written report must be sent to the Washington University Sponsor-Investigator and designee within **4 calendar days (for fatal or life threatening suspected adverse reactions) or 11 calendar days (for serious unexpected, suspected adverse reaction)** of the occurrence of the event or notification of the secondary site's PI of the event. The death of a research participant that qualifies as a reportable event should be reported within **1 working day** of the occurrence of the event or notification of the secondary site's PI of the event.

The research team at a secondary site is responsible for following its site's guidelines for reporting applicable events to its site's IRB according to its own institutional guidelines. The research team at Washington University is responsible for reporting all applicable events to the FDA, and Janssen.

### 7.4 Reporting to Secondary Sites

The Washington University Sponsor-Investigator (or designee) will notify the research team at each secondary site of all unanticipated problems involving risks to participants or others that have occurred at other sites within 10 working days of the occurrence of the event or notification of the Sponsor-Investigator (or designee) of the event. This includes events that take place both at Washington University and at other secondary sites, if applicable. Refer to Section 16.0 (Multicenter Management) for more information.

### 7.5 Reporting to Janssen

#### A. Overview

As the sponsor of the Study, the principal investigator shall be solely responsible for complying, within the required timelines, any safety reporting obligation to competent Health Authorities, IRB/ECs and any participating (co or sub) investigators, as defined in applicable laws and regulations. For the purposes of this section, safety data includes adverse events, product quality complaints (PQCs), and special situations including pregnancies.

The principal investigator will provide safety information to Janssen Scientific Affairs, LLC on adverse events, special situations including pregnancies and product quality complaints as defined within this section.

## **B. Management of Safety Data**

This Study has been designated as an interventional study. As such, all adverse events, special situations including pregnancies and product quality complaints will be reported as described in this Exhibit from the time a subject has signed and dated an Informed Consent Form (ICF) until 30 days after the last documented use of a product under study within the study. All subsequent AEs and SAEs will be collected after this period if the Principal Investigator considers the AE/SAE to be causally-related to the use of the study drug.

For the purposes of this study, the J&J medicinal product is DACOGEN™ (decitabine).

## **C. Hospitalization**

For reports of hospitalization, it is the sign, symptom or diagnosis which led to the hospitalization that is the serious event for which details must be provided.

Any event requiring hospitalization or prolongation of hospitalization that occurs during the study must be reported as a serious adverse event, except hospitalizations for the following:

- Hospitalizations not intended to treat an acute illness or adverse event (e.g., social reasons such as pending placement in long-term care facility)
- Surgery or procedure planned before entry into the study. [Note: Hospitalizations that were planned before the start of data collection and where the underlying condition for which the hospitalization was planned has not worsened will not be considered serious adverse events. Any adverse event that results in a prolongation of the originally planned hospitalization is to be reported as a new serious adverse event.]
- For convenience, the investigator may choose to hospitalize the subject for the duration of the treatment period.

## **D. Maintenance of Safety Information and Procedure for Reporting**

All safety data should be maintained in a clinical database in a retrievable format. The principal investigator shall provide all adverse events, both serious and non-serious, in report format. However, in certain circumstances more frequent provision of safety data may be necessary, e.g. to fulfill a regulatory request, and as such the data shall be made available within a reasonable timeframe at Janssen Scientific Affairs, LLC request.

## **E. Procedures for Reporting Safety Data and Product Quality Complaints (PQCs) for Janssen Medicinal Products to Janssen Scientific Affairs, LLC**

All adverse events and special situations, whether serious or non-serious, related or not related, following exposure to a J&J medicinal product are to be documented by the investigator and recorded in the CRF and in the subject's source records. Investigators must record in the CRF their opinion concerning the relationship of the adverse event to a J&J medicinal product.

All (serious and non-serious) adverse events reported for a J&J medicinal product should be followed-up in accordance with clinical practice.

#### **F. SAEs, Adverse Events of Special Interest and Special Reporting Situations**

All serious adverse events that have not resolved by the end of the study, or that have not resolved upon discontinuation of the subject's participation in the study, must be followed until any of the following occurs:

- The event resolves
- The event stabilizes
- The event returns to baseline, if a baseline value/status is available
- The event can be attributed to agents other than the study drug or to factors unrelated to study conduct
- It becomes unlikely that any additional information can be obtained (subject or health care practitioner refusal to provide additional information, lost to follow-up after demonstration of due diligence with follow-up efforts)

The principal investigator will transmit all SAEs, Adverse Events of Special Interest, and special situations following exposure to a J&J product under study in a form provided by Janssen Scientific Affairs, LLC in accordance with Section 7.5.L Transmission Methods, in English **within 24-hours of becoming aware of the event(s).**

In the event the study is blinded, the principal investigator will submit an unblinded SAE or pregnancy exposure report to Janssen Scientific Affairs, LLC.

All follow-up information for serious adverse events that are not resolved at the end of the study or by the time of patient withdrawal must be reported directly by the principal investigator, **within 24 hours becoming aware,** to Janssen Scientific Affairs, LLC using the Janssen Scientific Affairs, LLC Serious Adverse Event Report

All available clinical information relevant to the evaluation of a related SAE, Adverse Events of Special Interest, serious ADR or special situation is required.

- The principal investigator is responsible for ensuring that these cases are complete and if not are promptly followed-up. A safety report is not considered complete until all clinical details needed to interpret the case are received. Reporting of follow-up information should follow the same timeline as initial reports.

- Copies of any and all relevant correspondences with regulatory authorities and ethics committees regarding any and all serious adverse events, irrespective of association with the J&J Product under study, are to be provided to Janssen Scientific Affairs, LLC using a transmission method in Section 7.5.L **within 24 hours of such report or correspondence being sent to applicable health authorities.**

### **Special Reporting Situations**

Safety events of interest for a J&J medicinal product that require expediting reporting and/or safety evaluation include, but are not limited to:

- Drug exposure during pregnancy (maternal and paternal)
- Overdose of a J&J medicinal product
- Exposure to a J&J medicinal product from breastfeeding
- Suspected abuse/misuse of a J&J medicinal product
- Inadvertent or accidental exposure to a J&J medicinal product
- Any failure of expected pharmacological action (i.e., lack of effect) of a J&J medicinal product
- Medication error involving a J&J medicinal product (with or without patient exposure to the J&J medicinal product, e.g., name confusion)
- Suspected transmission of any infectious agent via administration of a medicinal product
- Unexpected therapeutic or clinical benefit from use of a Janssen medicinal product

These safety events may not meet the definition of an adverse event; however, from a Janssen Scientific Affairs, LLC perspective, they are treated in the same manner as adverse events. Special situations should be recorded on the Adverse Event page of the CRF.

Any special situation that meets the criteria of a serious adverse event should be recorded on a Serious Adverse Event Report Form and be reported to Janssen Scientific Affairs, LLC **within 24 hours of becoming aware of the event.**

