### **7.7 Exceptions to Expedited Reporting**

Events that do not require expedited reporting as described in include:

- planned hospitalizations
- respite care
- events related to disease progression

Events that do not require expedited reporting must still be captured in the EDC.

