## **D. Life-Threatening Adverse Experience**

**Definition:** any adverse drug experience that places the subject (in the view of the investigator) at immediate risk of death from the reaction as it occurred, i.e., it does not include a reaction that, had it occurred in a more severe form, might have caused death. Disease progression should not be recorded as an adverse event or serious adverse event term.

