## APPENDIX C: Reporting Timelines

Expedited Reporting Timelines					
Event	HRPO	QASMC	FDA	IBC	Janssen
Serious AND unexpected suspected adverse reaction			Report no later than 15 calendar days after it is determined that the information qualifies for reporting	N/A	Report within 24-hours of becoming aware of the event(s).
Unexpected fatal or life-threatening suspected adverse reaction			Report no later than 7 calendar days after initial receipt of the information		Report within 24-hours of becoming aware of the event(s).
Unanticipated problem involving risk to participants or others	Report within 10 working days. If the event results in the death of a participant enrolled at WU/BJH/SLCH, report within 1 working day.	Report via email after IRB acknowledgment			
Major deviation	Report within 10 working days. If the event results in the death of a participant enrolled at WU/BJH/SLCH, report within 1 working day.				
A series of minor deviations that are being reported as a continuing noncompliance	Report within 10 working days.				
Protocol exception	Approval must be obtained prior to implementing the change				
Clinically important increase in the rate of a serious suspected adverse reaction of			Report no later than 15 calendar days after it is determined that the information qualifies for reporting		

Expedited Reporting Timelines					
Event	HRPO	QASMC	FDA	IBC	Janssen
that list in the protocol or IB					
Complaints	If the complaint reveals an unanticipated problem involving risks to participants or others OR noncompliance, report within 10 working days. If the event results in the death of a participant enrolled at WU/BJH/SLCH, report within 1 working day. Otherwise, report at the time of continuing review.				
Breach of confidentiality	Within 10 working days.				
Incarceration	If withdrawing the participant poses a safety issue, report within 10 working days.  If withdrawing the participant does not represent a safety issue and the patient will be withdrawn, report at continuing review.				
SAEs, and Adverse Events of Special Interest and Special Reporting Situations (See Section 7.5.F)					Report within 24-hours of becoming aware of the event(s).
Pregnancy					Report within 24-hours of becoming aware of the event(s).

Routine Reporting Timelines				
Event	HRPO	QASMC	FDA	Janssen

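### Section 7.7 exempts progression-related events from expedited reporting, but 7.3, 7.5.C, 7.5.F and the Appendix A note on deaths require it; the coding of progression deaths and the SAE definition also conflict

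*Combined protocol and SAP*

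**What the plan says.** - **Section 7.7** lists three kinds of event that need no expedited reporting. The third is "events related to disease progression". The cross-reference that should say which reporting is meant is blank. Exempt events must still be entered in the EDC.
- **Section 7.5.C**: "Any event requiring hospitalization or prolongation of hospitalization that occurs during the study must be reported as a serious adverse event". Its three exceptions are admissions not for acute illness, procedures planned before entry, and admission for convenience.
- **Appendix A, note under item A**: a death from any cause is to be reported as an SAE.
- **Section 7.3**: secondary sites notify the coordinating center of all SAEs within 1 working day.
- **Section 7.5.F**: "The principal investigator will transmit all SAEs, Adverse Events of Special Interest, and special situations following exposure to a J&J product under study", with a 24-hour limit that Appendix C repeats.
- **Appendix A, item A** defines an SAE so as to leave out events related to infection, bleeding or a transfusion reaction.
- **Appendix A, item D**: "Disease progression should not be recorded as an adverse event or serious adverse event term". **Section 11.1** says a death from progression goes on the Toxicity Form as a grade 5 event under that term.
- **Section 7.5.F, Special Reporting Situations** includes "Any failure of expected pharmacological action (i.e., lack of effect) of a J&J medicinal product" and adds: "Special situations should be recorded on the Adverse Event page of the CRF".

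**The concern.** Sites need one answer to two questions: who is told of a serious event, and how fast. For an event attributed to progression, the protocol gives opposite answers in different sections. The choice then rests on the site's attribution, in a disease where infection, cytopenia and leukemia act together. An admission that one site reports the next working day can be left to routine data entry at another. The same death can be a grade 5 toxicity at one site and not an adverse event at another, which makes the safety tables hard to interpret.

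**Working it through.** The plan gives no figure on this point, so there is nothing to reproduce. The check sets the provisions side by side.

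| Event | Provisions that expedite | Provisions that do not | Result |
|---|---|---|---|
| Admission labelled progression | 7.5.C with 7.3 (1 working day) and 7.5.F (24 hours) | 7.7; Appendix C then leaves secondary sites to routine data entry | Conflict |
| Death labelled progression, to the drug company | Appendix A note; 7.5.F; 7.0, which says the company's reports follow 7.5 | 7.7, no recipient named | Expedited on the better reading |
| Death labelled progression, to the coordinating center | Appendix A note with 7.3 | 7.7 | Conflict |
| Admission for sepsis, no progression label | 7.5.C with 7.5.F | Appendix A item A | Conflict |

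1. **Recipients.** Section 7.6 asks the FDA reports to cover suspected adverse reactions, and Appendix C asks for unanticipated problems to go to the HRPO. An event correctly attributed to progression would not ordinarily be either. The conflict therefore lies in reports to the coordinating center and the drug company.

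2. **Exceptions.** The planned admissions and respite care in 7.7 have counterparts among the 7.5.C exceptions. Progression has none.

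3. **Deaths under 7.3.** Its separate sentence on deaths covers only a death that qualifies as a reportable event, which leads back to the question of whether 7.7 applies.

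4. **SAE definition.** Section 7.3 points to Appendix A for what counts as serious. It cites item D, the life-threatening definition, although the SAE definition is item A. Item A excludes infection and bleeding, so a septic admission can drop out of 7.3 even if nobody calls it progression. The note restores deaths, but nothing restores admissions.

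5. **Attribution.** Section 1.3 puts deaths in the first 8 weeks at 15-17%, mostly from infection and cytopenias that it ties to both disease and therapy. If that rate applied to 60 patients: 60 x 0.15 = 9.0 and 60 x 0.17 = 10.2, or about 9 to 10 early deaths. This shows how often the cause may be hard to assign. It does not count reports that would be missed.

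6. **Coding.** Section 11.1 requires, for a progression death, the term that Appendix A item D forbids. Appendix A also plans a summary of treatment-emergent adverse events by patient count, percent, attribution and grade. Whether such deaths appear there as grade 5 events depends on which instruction is followed.

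7. **Lack of effect.** The term is not defined. Its only other use is in 7.5.I, on product quality complaints, beside lot numbers and quarantine of product. Nothing links it to the response categories of Section 12, and nothing excludes them.

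**The case against.** Section 7.0 says the drug company's reports follow 7.5, and the Appendix A note covers every death. Section 11 also asks for the Death Form at death, the Hospitalization Form at admission and the adverse event record when the event occurs. On that view little is lost. This stands for deaths reported to the drug company, and it stands against any claim that events go unrecorded. It does not resolve 7.3 against 7.7 for the coordinating center. It does not cure the SAE definition for admissions, and filing a form is not the same as notifying someone within 1 working day.

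A reader might infer three stronger things, none of which the documents support:

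- **Early deaths are first seen in the six-monthly DSM report.** The note, 7.0, 7.5.F and the form schedule in Section 11 all point to earlier reporting or capture.
- **Every non-responder becomes an adverse event case.** At the 10-15% CR/CRi rate in Section 2.2 that would be 60 x 0.85 = 51 to 60 x 0.90 = 54 patients. But that is the historical-control rate, whereas Section 1.2 reports responses in 21 of 21 *TP53*-mutated patients given decitabine. The count also includes PR and mLFS, and it assumes that lack of effect means non-response. Entry on the adverse event page is explicit. Entry into the incidence tables is only inferred, because 7.5.F says special situations may not meet the adverse event definition.
- **Section 7.5.F directly contradicts Appendix A item D.** Item D bars a term. An entry called lack of effect could satisfy both, and stable disease is not progression.

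**Conclusion.** The concern holds as a conflict in safety reporting and coding. Expedited reporting of a progression-labelled admission depends on the section followed and on the site's attribution. So does that of a progression-labelled death, for recipients other than the drug company. Progression deaths have two incompatible coding rules, and the Appendix A SAE definition is narrower than 7.5.C. The undefined lack-of-effect category is secondary.

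The number of patients affected cannot be derived, because the documents do not say how many deaths or admissions sites will attribute to progression or infection. The conclusion rests on 7.7 applying to any recipient, which its wording and blank cross-reference leave open. The primary 1-year survival analysis is unaffected, since it counts deaths from any cause. The change is worth making because it is cheap and concerns prompt review of serious events.

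**What to change.** 1. **Section 7.7.** Fill in the cross-reference and name the recipients. State that the progression exemption does not cover deaths, or hospitalizations that 7.5.C makes SAEs, so that 7.3 and 7.5.F apply whatever cause is assigned.
2. **Appendix A item A.** Align the SAE definition with 7.5.C so that admissions for infection or bleeding are not dropped, and correct the pointer in 7.3. Without this step, the change to 7.7 would not bring septic admissions into 7.3.
3. **Section 11.1 and Appendix A item D.** Choose one coding rule for progression deaths and tabulate them apart from treatment-emergent adverse events.
4. **Section 7.5.F.** Agree with the drug company whether Section 12 outcomes count as lack of effect, write the answer down, and keep any such entries out of the adverse event incidence tables.

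The cost is a few sentences of protocol text, the drug company's agreement on item 4, and a few more expedited reports. No analysis of survival or response changes.
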